Treatment of HCV has been the main focus of clinical research since vaccine research has proved to be difficult, as well as the necessity of treating undiagnosed individuals. Among the 7 major HCV genotypes, genotype 1 is by far the most prevalent in Europe and in the United States. It has historically been the most difficult type to treat. Prior to 2011, the standard treatment for HCV was a combination of once-weekly injectable Pegylated Interferon with daily

oral Ribavirin to be taken for 48 weeks. The cure rate, measured as sustained virologic response (SVR) for this regimen is a dismal 40-50% [6]. Adherence to the treatment was difficult for many patients due to the length of therapy and the associated side effects of both interferon and ribavirin. The addition of new directly acting agents (DAA), Boceprevir and Telaprevir in 2011, revolutionized HCV treatment, increasing cure rates up to 75%. However, adherence continued to plague therapy because of side effects and thrice-daily dosing.

In 2013, 2 new DAA's were FDA-approved, ushering in the interferon-free era of HCV therapy. Sofosbuvir and Simprevir are once daily oral agents with much fewer side effects than any previous anti-HCV medication. Ledipasvir, another oral DAA, has been approved by the FDA in October 2014, to be given as a single tablet regimen together with Sofosbuvir. The length of treatment has also decreased, from 48 weeks to 12-24 weeks, and clinical trials of the combination of these drugs showed cure rates above 90%, with increased tolerability and safety [8]. Other DAA's since then have been approved by the FDA such as the combinations of ombitasvir/paritaprevir/ritonavir (Viekira Pak) and Grazopravir/Elbasvir (**Zepatier**).

are in clinical trials or under FDA review, increasing the chances that more patients can be cured from HCV infection.

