Adherence, however, has been a major challenge in the treatment of Hepatitis C infection, especially before Sofosbuvir and Simprevir were introduced. Aside from side effects, Ribavirin has to be taken twice daily, while Interferon is injectable. Boceprevir and Telaprevir also had their fair share of side effects, drug interactions and multiple daily dosing which impaired treatment adherence. Studies on these medications have shown that the proportion of missed doses increases over time, and are associated with failure of treatment [11-14]. In one analysis of 2 clinical trials, patients who took their medications $\geq 80-85\%$ of the time achieved SVR 86-90% of the time, while those $< 80\%$ adherent attained SVR only 8-32% of the time [28]. Aside from HCV medication-related issues, these patients may have other co-morbidities such as psychiatric disorders which can negatively influence patient compliance [18]. The matter of polypharmacy in patients co-infected with HIV and HCV can also be a major concern in terms of adherence [19].

Treatment adherence studies for Hepatitis C were mostly small studies of patients taking Pegylated-Interferon and Ribavirin [11-14]. These reports showed higher treatment success for patients who were at least 80-90% compliant, with most failures reported in patients with compliance rate around 70-80%. However, most of these also relied on patient self-reporting, pill counting and pharmacy refill data, which are inherently imprecise.

With the enhanced tolerability, lower drug-drug interactions, side effect profile and once daily dosing of the new DAA's, adherence has improved but is still an area of concern. In registration clinical trials, those who relapsed on Sofosbuvir were patients who did not comply to their treatment regimen [15]. The same holds true for Simeprevir, and these patients also developed resistant HCV [16]. With the standard 12-weeks course of these medications costing in the range

of \$100,000 - \$140,000, patients needing repeat treatment after relapsing can be very expensive [10], making treatment compliance even more important. It would also be very costly for treatment-experienced patients to be re-treated because of failure due to compliance.

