Electronic assisted compliance is not the sole indicator of MEMS, it is also used in conjunction with answers about demographics, clinical state and symptoms to learn more about the patient characteristics that influence whether a medication regimen is adhered to.

Portal724-MEMS is HIPAA Complaint and ISO27001 Certified. The Electronic Data Capture, the Data Transfer and Data Access are all confidential and Secure in every stage of the Data

Flow Model. The device to be used in this study is a Smart Cap with Pill Dispensing and Integrated Cellular Modem.

Objective

Primary: To determine the effect of the use of Portal724-MEMS Service on medication adherence in the treatment of Hepatitis C patients with grazopravir/elbasvir with or without Ribavirin, defined as compliance to regimen 95% of the time.

Methods

Study design: Open-label, randomized, single center pilot study.

Treatment Arms:

Genotype 1a, treatment naïve or PegIFN/RBV experienced without baseline NS5A polymorphisms with elbasvir/grazoprevir for 12 weeks

Genotype 1a, treatment naïve or PegIFN/RBV experienced with baseline NS5A polymorphisms with elbasvir/grazoprevir/ribavirin for 16 weeks

Genotype 1b, treatment naïve or PegIFN/RBV experienced for 12 weeks

Genotype 1a or 1b, PegIFN/RBV/PI-experienced with elbasvir/grazoprevir/ribavirin for 16 weeks

Genotype 4: treatment naïve with elbasvir/grazoprevir for 12 weeks

Genotype 4: PegIFN/RBV- experienced with elbasvir/grazoprevir/ribavirin for 16 weeks

Proposed number of participants: 40 patients infected with HCV (20 for each group)

Data Collection Time Period: approximately 1 year

Site of Enrollment:

Liver Center at Saint Michael's Medical Center. [name].

In the Liver Center, the main Hepatitis / Infectious Diseases Physician that this study will collaborate with is [name], MD.

Study Patient Population

Treatment-naïve and treatment-experienced genotype 1 and 4 HCV patients with or without compensated cirrhosis will be enrolled in this study.

The inclusion criteria for study are as follows:

1. Male or female 18 years old and above.
2. Be HCV treatment naïve
3. HCV RNA PCR \geq 10,000 IU/L
4. Confirmed infection with Hepatitis C virus (HCV) by HCV serum antibody assay and by HCV Ribonucleic Acid (RNA) Polymerase Chain Reaction (PCR) and Confirmed chronicity with 2 PCR's 6 months apart.
5. Patients with HCV Genotype 1, 4

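### Inclusion criterion 2 admits only treatment-naive patients, contradicting the stated population and five of six regimen rows (two emptied, three narrowed); exclusion 7 is also worded in reverse

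*Combined protocol and SAP*

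**What the plan says.** Study Patient Population opens with: "Treatment-naïve and treatment-experienced genotype 1 and 4 HCV patients with or without compensated cirrhosis will be enrolled in this study". The numbered inclusion list directly below it then requires, as criterion 2, "Be HCV treatment naïve".

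Treatment Arms, under Methods, lists six regimen rows by genotype, treatment history and, for genotype 1a, NS5A polymorphisms. Two of them are for experienced patients only: "Genotype 1a or 1b, PegIFN/RBV/PI-experienced with elbasvir/grazoprevir/ribavirin for 16 weeks" and "Genotype 4: PegIFN/RBV- experienced with elbasvir/grazoprevir/ribavirin for 16 weeks". Three admit either naive or PegIFN/RBV-experienced patients, and one (genotype 4, 12 weeks) admits naive patients only.

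The primary objective concerns "medication adherence in the treatment of Hepatitis C patients with grazopravir/elbasvir with or without Ribavirin".

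Separately, exclusion criterion 7 lists untreated psychiatric conditions that, in the principal investigator's opinion, will *not* interfere with visits or procedures. It stands under a lead-in by which meeting any listed item excludes the patient.

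**The concern.** Screening staff cannot follow both texts. A PegIFN/RBV-experienced patient fits the population sentence and has a regimen row, but fails a numbered inclusion criterion. Staff must either turn away patients for whom the design provides a regimen, or enrol them and record a deviation each time.

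The choice also determines what the trial describes. Under a naive-only rule, the adherence and SVR results apply only to naive patients, and the ribavirin-containing regimens within the primary objective rest on a single row. The Introduction lists ribavirin's dosing among the adherence problems of earlier treatment ("Ribavirin has to be taken twice daily, while Interferon is injectable"), so the regimen mix could matter for an adherence outcome.

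Exclusion 7 is a lesser problem of the same kind. The Introduction refers to "psychiatric disorders which can negatively influence patient compliance", and compliance is the primary outcome. Yet the criterion as worded removes the patients judged unlikely to cause difficulty and does not itself remove those judged likely to.

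**Working it through.** There is no planned figure to reproduce. The check is a count of the Treatment Arms rows against inclusion 2, followed by a reading of the text.

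**Rows under Treatment Arms, in the order listed**

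| Row | Genotype | Treatment history admitted | Duration | Ribavirin named | Effect of inclusion 2 |
|---|---|---|---|---|---|
| 1 | 1a, no NS5A polymorphisms | naive or PegIFN/RBV | 12 wk | no | naive patients only |
| 2 | 1a, NS5A polymorphisms | naive or PegIFN/RBV | 16 wk | yes | naive patients only |
| 3 | 1b | naive or PegIFN/RBV | 12 wk | no | naive patients only |
| 4 | 1a or 1b | PegIFN/RBV/PI | 16 wk | yes | no eligible patient |
| 5 | 4 | naive | 12 wk | no | unaffected |
| 6 | 4 | PegIFN/RBV | 16 wk | yes | no eligible patient |

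**Counts**

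- Rows naming experienced patients: 3 (rows 1, 2, 3) + 2 (rows 4, 6) = 5 of 6.
- Rows emptied: 2 (rows 4, 6). Rows narrowed: 3 (rows 1, 2, 3). Rows unaffected: 1 (row 5). 2 + 3 + 1 = 6.
- 16-week ribavirin rows that can still be filled: 3 − 2 = 1 of 3, and that one only by naive genotype 1a patients with NS5A polymorphisms.
- 12-week rows that can still be filled: 3 − 0 = 3 of 3.

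**Can the criterion be read so that the conflict disappears?** It would have to mean naive to the newer oral drugs. The criterion speaks of HCV treatment in general. The Introduction states "Prior to 2011, the standard treatment for HCV was a combination of once-weekly injectable Pegylated Interferon with daily" oral ribavirin, so in the protocol's own terms a patient previously given that combination has had HCV treatment. Inclusion 7 asks only that patients be candidates for oral direct-acting agents and does not modify inclusion 2. No other section corrects the criterion.

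**Sample size.** The plan is 40 patients, 20 per group, with no target by row. Emptying rows therefore leaves the total unchanged. The expected share of experienced patients is not given, so slower recruitment cannot be quantified.

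**Between-arm comparison.** Enrollment randomises eligible patients 1:1 to the two arms. Either version of the rule would apply equally to both, so the contradiction does not bias the comparison.

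**Exclusion 7.** Combining the lead-in with the item gives: excluded if the condition is untreated and judged not to interfere. A patient whose untreated condition is judged to interfere does not meet the item. Exclusion 2 (unsuitable in the treating physician's view), exclusion 8 (untreated substance abuse), exclusion 11 (unwilling to follow medication instructions) and inclusion 8 (understanding and consent) would catch some of these patients, but not all of them by rule.

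**The case against.** The strongest reply is that this is a recognisable drafting slip. The population sentence, five regimen rows, and the 12-or-16-week, with-or-without-ribavirin wording in Enrollment are all consistent with a mixed population, against one four-word line. There is no between-arm bias, the total is unchanged and the remedy is wording only. These facts are correct, and they mean the problem is one of eligibility and generalisability rather than a threat to the primary comparison. They do not remove it: patients are screened one by one against the numbered criteria, and this criterion is the operative line.

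A second objection is that the ribavirin consequence should not be pressed. No ribavirin stratum, subgroup analysis or row target is planned. The remark on twice-daily dosing comes from a paragraph mainly about older treatment, and Enrollment describes study treatment as one tablet daily. This largely stands: no planned analysis is lost. What remains is that the regimens over which adherence is measured differ according to which text is followed.

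On exclusion 7, other criteria narrow the practical gap, and the protocol does not allow an estimate of how many patients remain. Item 15 of the same list also reads oddly under the lead-in, since it would literally exclude women who agree to contraception. That points to loose drafting of the whole list; it does not make item 7 correct.

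**Conclusion.** The concern holds. Inclusion 2 is incompatible with the population sentence and with five of the six regimen rows: totally for two, partially for three. Applied literally, it leaves one of three 16-week ribavirin rows and all three 12-week rows with eligible patients. The protocol therefore gives two answers to who may be randomised. The conflict arises the first time an experienced patient is screened, and analysis cannot repair it afterwards.

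The conclusion rests on reading the criterion as written, with prior PegIFN/RBV counted as HCV treatment, as the Introduction does. It does not depend on any assumed share of experienced patients. The need to correct the plan before use rests on inclusion 2 alone; the reversed wording of exclusion 7 is real but secondary.

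**What to change.** Reconcile inclusion 2, the population sentence and the Treatment Arms list so that all three describe the same patients. The population sentence and the list both point to admitting naive patients together with those who have had the prior regimens listed; if so, reword inclusion 2 to say that. If the sponsor intends a naive-only trial, amend the population sentence and the regimen list instead. The sponsor must state which is meant.

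In the same amendment, correct exclusion 7 so that it excludes conditions judged to interfere with visits or procedures, either by deleting *not* or by inserting *unless* and keeping *not*. The two differ mainly in what happens when no opinion is recorded, so the sponsor should confirm the intended wording.

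The cost is a protocol wording amendment, with no additional patients or procedures.

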6. Genotype 1a patients will be required to have historical resistance-associated variants (RAV) testing or done at screening if not previously performed
7. Patients are candidates for treatment of HCV with oral Direct-Acting Agents (DAA)
8. understand the study procedures, alternative treatments available, risks involved with the study, and voluntarily agrees to participate by giving written informed consent
9. Abstain from sexual intercourse will taking study medications and for 14 days after the last dose of study medications

Patients will be excluded from the study if they fulfill any of the following criteria:

1. Patient not willing to sign written informed consent
2. Patients deemed not suitable for HCV treatment as deemed by the treating physician at the liver center
3. Patients with decompensated liver cirrhosis, defined as follows:
 - a. Liver biopsy within the last year showing Scheuer Stage 4 or transient elastography (Fibroscan®) in the last year with a reading of >12.5 kPa;

AND

- b. Any clinical sign of hepatic decompensation such as ascites (fluid in the abdomen), jaundice (yellowing of eyes and skin), esophageal varices with bleeding (enlarged veins of the esophagus seen on endoscopy) or hepatic encephalopathy (tremors, confusion, sleepiness)
4. Co-Infection with the Hepatitis B virus
5. Any liver disease of non-HCV etiology such as Hemochromatosis, Wilson's Disease, Alcoholic liver disease or Non-Alcoholic Steato-Hepatitis (NASH)
6. Hepatocellular carcinoma or any other malignancy
7. Untreated psychiatric conditions such as major depression, schizophrenia, bipolar disorder which in the opinion of the Principal Investigator will not interfere with protocol visit and/or procedures
8. Current and untreated substance abuse (cocaine, opiates, alcohol, marijuana, other recreational drugs, controlled substances)
9. Patient is pregnant or breastfeeding.
10. Patients unwilling to use cellular phones
11. Patients unwilling to follow specific instructions for medication intake
12. Patient has any of the following conditions:
 - Organ transplants (including hematopoietic stem cell transplants) other than cornea and hair.
 - Poor venous access that precludes routine peripheral blood sampling required for this trial.
 - History of gastric surgery (e.g., stapling, bypass) or subject with a history of malabsorption disorders (e.g., celiac sprue disease).

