 - History of a medical/surgical condition that resulted in hospitalization within the 3 months prior to enrollment, other than for minor elective procedures
 - Medical/surgical conditions that may result in a need for hospitalization during the period of the study
 - Any medical condition requiring, or likely to require, chronic systemic administration of corticosteroids, TNF antagonists, or other immunosuppressant drugs during the course of the trial
13. has exclusionary laboratory values as listed below:
 - Noncirrhotic/Cirrhotic Subjects**
 - Creatinine clearance < 50 mL/min
 - Hemoglobin <9.5 g/dL for both male and female subjects
 - Platelets <50 x 10³/μL
 - serum albumin < 3.0 g/dL
 - INR >1.7, unless subject has a stable INR on an anticoagulant regimen.
 - HbA1c >10%
 - ALT >10XULN
 - AST >10XULN

14. is or has an immediate family member (e.g., spouse, parent/legal guardian, sibling or child) who is investigational site or sponsor staff directly involved with this trial.

15. agree to the following:

- The subject is a female who is not of reproductive potential, defined as a female who either: (1) is postmenopausal (defined as at least 12 months with no menses in women \geq 45 years of age); (2) has had a hysterectomy and/or bilateral oophorectomy, bilateral salpingectomy, or bilateral tubal ligation/occlusion at least 6 weeks prior to screening; OR (3) has a congenital or acquired condition that prevents childbearing.

- The subject is a female who is of reproductive potential and agrees to avoid becoming pregnant while receiving study drug and for 14 days after the last dose of study drug by complying with one of the following: (1) practice abstinence† from heterosexual activity OR (2) use (or have her partner use) acceptable contraception during heterosexual activity. Acceptable methods of contraception are‡:

Single method (one of the following is acceptable):

- intrauterine device (IUD)
- vasectomy of a female subject's male partner
- contraceptive rod implanted into the skin

Combination method (requires use of two of the following):

- diaphragm with spermicide (cannot be used in conjunction with cervical cap/spermicide)
- cervical cap with spermicide (nulliparous women only)
- contraceptive sponge (nulliparous women only)
- male condom or female condom (cannot be used together)

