- hormonal contraceptive: oral contraceptive pill (estrogen/progestin pill or progestinonly pill), contraceptive skin patch, vaginal contraceptive ring, or subcutaneous contraceptive injection

†Abstinence (relative to heterosexual activity) can be used as the sole method of contraception if it is consistently employed as the subject's preferred and usual lifestyle and if considered acceptable by local regulatory agencies and ERCs/IRBs. Periodic abstinence (e.g., calendar, ovulation, sympto-thermal, post-ovulation methods, etc.) and withdrawal are not acceptable methods of contraception.

0455LH

Enrollment

Upon signing the informed consent, the following data will be gathered prior to start of treatment: demographic data such as age, gender, race/ethnicity, highest educational attainment, employment status, co-morbid conditions as documented in the patient's records, current medications, vital signs (blood pressure, heart rate, respiratory rate, temperature), CBC with differential count, complete metabolic panel, 12-Lead Electrocardiogram (EKG), Cardiac stress test results if applicable, echocardiogram results if applicable, , BMI, baseline HCV RNA PCR

viral load, HCV genotype, baseline HCV resistance testing (if indicated), results of the Fibroscan® test or liver biopsy.

Once the informed consent is signed and the patient is deemed eligible for treatment, the patient will be randomized to either ARM 1 or ARM 2 in a 1:1 ratio. ARM 1 will be prescribed elbasvirir/grazoprevir with/or without ribavirin for 12 or 16 weeks 1 tablet daily with MEMS Smart Cap with real-time monitoring. Arm 2: elbasvir/grazoprevir with/or without ribavirin for 12 or 16 weeks 1 tablet daily MEMS Smart Cap without real-time monitoring.

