For Group 1, the cap of the study drug bottle will be replaced with the Portal724- MEMS Smart Cap. A cellular phone per patient will also be provided. The Smart Cap in this study is to be outfitted to send messages to a website to which only the investigators and the research assistants have access to monitor medication adherence. Patients are to be instructed to open their study drug bottles in areas where there is at least 1 cellular signal bar. Patients will also be instructed to take their medications at specific agreed upon times. Once the agreed upon times are set, these will be programmed into the Smart Caps through a software program. The Smart Caps are encoded to not only record each pill bottle opening, it also will transmit an alert to the aforementioned website when the bottle is not opened within 2 hours of the agreed upon time. This alert is then seen by the Investigator or the Research assistant through a computer or their smartphone. The Investigator or Research Assistant in turn calls the cellular phone provided to the patient to remind the participant to take their medication, thus providing real-time feedback. Group 2 (the control group) will be provided MEMS Smart Cap to record study drug bottle opening, but without real-time feedback and will be managed as per the standard of care at the Liver Center SMMC.

Patients from both groups will be seen in the Liver Center at Day 1, weeks 2, 4, 8 and 12 from start of treatment. They will be seen by Liver Center Physician together with the Investigator and Research Assistant at each visit. They will also be counseled about the importance of medication adherence at every visit by the Liver Center physician. At each visit, patients are instructed to bring with them all of their anti-HCV study drug bottles for pill counting to be done by the Investigator and Research Assistant. Patients in ARM 1 will also get feedback about their medication compliance using the Smart Caps per visit.

After completion of treatment as determined by the Liver Center Physician, patients from both groups are to follow-up at week 4 and week 12 post-treatment. At that time, an HCV RNA PCR viral load will be obtained to determine if patient has an undetectable viral load, or Sustained Virologic Response (SVR). SVR is the marker for a functional cure of HCV, or treatment success. Non-SVR would mean treatment failure.

Study Procedures	Pre-Treatment						Treatment Assessments		Post Tx	Post tx

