Fourteen patients have discontinued the MK-5172 therapy early due to a side effect. In some cases the patients discontinued only MK-5172 and in other cases the patients discontinued all therapy. The side effects that led to the study drug being stopped included decrease in the blood cells that carry oxygen, increased bilirubin, low blood pressure, weakness, headache, flu-like illness, irritability, shortness of breath, dehydration, fear/nightmares, anxiety/depression, increased levels of transaminases, nausea, reactivation of chronic pancreatitis (inflammation of an abdominal gland) and myositis (inflammation of the muscles). Not all of these side effects were considered to be related to MK-5172.

Ribavirin

COMMON ADVERSE EVENTS

The most common side effects when taking ribavirin combined with pegylated interferon are flu-like symptoms consisting of:

- Body aches and pains
- Fever
- Chills
- Headache
- Overall feeling of sickness
- Rash

Other common side effects are: anxiety, mood changes, depression and irritability.

The most serious side effect seen with RBV is anemia (a decrease in the number of red blood cells in your body that carry oxygen). Which may cause tiredness and lack of energy. Other side effects may occur which are not listed here or were not seen before.

Ribavirin can cause severe damage and even death of an unborn child or fetus. **Extreme care should be taken to prevent pregnancy while you are taking RBV and afterwards. Patients will be required to abstain from sexual course while taking ribavirin and for 6 months after the last dose of ribavirin**

DILI

In the event of a discontinuation of grazoprevir/elbasvir for suspected ***DILI***, other clinically significant liver chemistry elevations (defined under "Liver Chemistry Stopping and Follow up Criteria", below), severe skin reaction or hypersensitivity reaction, subjects should not restart grazoprevir/elbasvir due to the risk of a recurrent reaction; such subjects should be withdrawn from study and seek/be reviewed for alternative HCV therapy.

Allergic Reaction

Subjects may continue study medication for Grade I or 2 allergic reactions at the discretion of the Investigator. The subject should be advised to contact the Investigator immediately if there is any worsening of symptoms or if further systemic signs or symptoms develop. Antihistamines, topical corticosteroids, or antipruritic agents may be prescribed.

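### Inclusion criterion 9 sets 14 days of post-treatment abstinence with no ribavirin exception, while the Ribavirin section requires 6 months

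*Combined protocol and SAP*

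**What the plan says.** Three places in the combined protocol and SAP govern sexual activity or pregnancy after treatment.

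- **Study Patient Population, inclusion criterion 9**, for all patients: "Abstain from sexual intercourse will taking study medications and for 14 days after the last dose of study medications".
- **Study Patient Population, exclusion list, item 15**, for women of reproductive potential. The subject "agrees to avoid becoming pregnant while receiving study drug and for 14 days after the last dose of study drug", either by abstinence or by listed contraception.
- **Toxicity management, Ribavirin**: "Patients will be required to abstain from sexual course while taking ribavirin and for 6 months after the last dose of ribavirin". The reason is given just before: "Ribavirin can cause severe damage and even death of an unborn child or fetus".

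Neither eligibility item mentions ribavirin or points to the Ribavirin section, and the Ribavirin section does not point back. Under Enrollment, both randomized arms receive elbasvir/grazoprevir with or without ribavirin, for 12 or 16 weeks. After treatment, "patients from both groups are to follow-up at week 4 and week 12 post-treatment".

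**The concern.** A patient on a ribavirin regimen is given two different end dates for the same restriction, and no text says which one governs. The shorter date stands in the eligibility criteria, where patients are screened and make their commitment. The longer one stands only under toxicity management. A ribavirin patient can therefore meet the entry criteria by agreeing to a period that the protocol elsewhere treats as far too short. For women of reproductive potential the kind of restriction may differ as well, since item 15 accepts contraception where the Ribavirin section demands abstinence.

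What is at stake is exposure of a pregnancy to ribavirin, which the protocol itself describes as potentially fatal to the fetus. No estimate, test or sample size depends on this point.

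**Working it through.** The protocol gives no day count for the longer period, so there is no figure to reproduce. The check is a comparison of texts plus day arithmetic.

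**Inputs**

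- Eligibility period: 14 days (inclusion 9; same figure in item 15).
- Ribavirin period: 6 months (Toxicity management, Ribavirin).
- Ribavirin regimens last 16 weeks (Treatment Arms).
- Post-treatment visits: weeks 4 and 12 (Enrollment and the study procedures table).
- Assumption: both drugs end on the same day, after a full course.

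**Difference between the two periods**

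- 6 months = 365.25 / 2 = 182.6, about 183 days (181 to 184, depending on the calendar months).
- Difference = 183 − 14 = 169 days (181 − 14 = 167 to 184 − 14 = 170).
- If ribavirin is stopped early while elbasvir/grazoprevir continues, the difference shrinks by the number of days between the two last doses. That number cannot exceed 16 × 7 = 112, so the difference is never below about 169 − 112 = 57 days. The ribavirin rule always ends later.

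**Position of the visits, in days after the last dose**

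| Event | Day |
|---|---|
| 14-day period ends | 14 |
| Post-treatment week 4 visit | 4 × 7 = 28 |
| Post-treatment week 12 visit (last) | 12 × 7 = 84 |
| 6-month ribavirin period ends | about 183 |

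The first post-treatment visit comes 28 − 14 = 14 days after the shorter period has lapsed. About 183 − 84 = 99 days (97 to 100) of the longer period fall after the last visit. The end-of-treatment visit (week 12/16 column of the study procedures table) falls before either period has run.

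**Regimens touched**

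Treatment Arms lists six regimens. Ribavirin is in three: genotype 1a with baseline NS5A polymorphisms; genotype 1a or 1b with protease-inhibitor experience; genotype 4 with PegIFN/RBV experience. That is 3 of 6. Inclusion criterion 2 admits only treatment-naïve patients, although the opening of Study Patient Population also admits experienced ones. If criterion 2 is applied strictly, the second and third of these have no eligible patients. The first also takes treatment-naïve patients, so 1 of 6 remains and the conflict does not disappear.

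**Do the terms separate the rules?**

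Neither study medications (inclusion 9) nor study drug (item 15) is defined. Item 15 uses the singular, and the Introduction names grazoprevir/elbasvir as the drug to be used. Item 15 can therefore be read as covering that tablet only, in which case it and the Ribavirin section concern different drugs. Inclusion 9 uses the plural and applies to everyone, and ribavirin is part of the prescribed treatment in both arms. Nothing takes ribavirin out of its scope. It is also the only eligibility rule on this matter that reaches men.

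**The case against.** The strongest reply is that the safeguard is already there. The Ribavirin section is mandatory, specific to the drug, addressed to all patients, and gives its reason. The two periods can both be met: a patient who abstains for 6 months has also abstained for 14 days. Nothing in the eligibility text says that restrictions end at day 14 for ribavirin patients. On this view the criteria set a general minimum, the Ribavirin section adds a longer rule for one drug, and only a cross-reference is missing.

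Much of this stands. A reader might infer from inclusion 9 that the protocol omits the 6-month precaution, and that would be wrong. A reader might also infer that ribavirin patients will be told 14 days. The documents do not show that: it depends on staff practice and on the consent form, which is not part of the text available for review. Nor do the 99 days after the last visit show that the visit schedule is inadequate. The date can be given at the end-of-treatment visit and repeated at post-treatment week 12, both already scheduled.

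The reply does not remove the contradiction. The general-minimum reading has to be supplied by the reader, because inclusion 9 states one period for study medications without qualification and never says that a longer one may apply. Staff who work from the eligibility list alone would fall short of the Ribavirin section on a fetal-harm precaution.

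Two further changes may be tempting but do not follow. One is to drop the blanket abstinence in inclusion 9 for regimens without ribavirin, because item 15 allows contraception. That is a matter of preference, and it would leave men on those regimens with no rule. The other is to restructure item 15, which is worded as an inclusion criterion but sits under "Patients will be excluded from the study if they fulfill any of the following criteria". That is editorial and separate from this point.

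**Conclusion.** The contradiction is real and is confined to the ribavirin regimens. Inclusion 9 is too short by the protocol's own standard: 14 days against about 183, a difference of about 169 days (167 to 170) when both drugs end together after a full course. Item 15 repeats the 14 days, but it is weaker evidence because its wording may cover elbasvir/grazoprevir only. For regimens without ribavirin, the 14-day period is consistent throughout.

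The 6-month rule exists and binds, so this is an internal inconsistency and not an absent safeguard. It touches 3 of the 6 regimens, or 1 of the 6 under strict use of inclusion criterion 2. The documents do not say how many of the 40 patients are expected to take ribavirin, so no number of affected patients can be given. The conclusion rests on reading study medications in inclusion 9 as including ribavirin, which the treatment description supports and no definition contradicts. The harm named in the protocol is severe and the correction is nearly free, so it should be made before any ribavirin patient is enrolled.

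**What to change.** 1. Add one clause to inclusion 9, and to the part of item 15 on women of reproductive potential, for example: *and, for patients whose regimen includes ribavirin, abstain from sexual intercourse throughout ribavirin treatment and until 6 months after its last dose (see Toxicity management, Ribavirin)*.
2. Add the return reference in the Ribavirin section, so that the two places name each other.
3. Check that the consent form states 6 months for ribavirin patients, and correct it if it does not.
4. At the end-of-treatment visit and again at post-treatment week 12, tell each ribavirin patient the calendar date on which the 6 months end.
5. Leave the existing 14-day rule unchanged for regimens without ribavirin.

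The cost is a small wording amendment, possibly with a consent-form change, submitted to the IRB. No visit is added, and sample size and analysis are unaffected.
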